### **11.8.3 Analysis for the secondary endpoints**

With regard to the secondary endpoints pertaining to the LCSS outcome measures, the mean change of the total LCSS, defined as the average value of all individual item scores, will be calculated from enrolment to all available subsequent study visits and will be examined for statistical significance with the use of the paired t-test or its non-parametric analogue. Similar analysis will be performed for the ASBI subscore and each individual domain of LCSS.

If applicable, pertaining to the change of the mean LCSS as well as the mean ASBI through the observation period, linear mixed models will be applied, in order to estimate the monthly predicted change in the aforementioned scores.

Additionally, the symptom improvement rate throughout the study observation period will also be calculated in patient-years.

The distribution of patients by level ('level 1: no problems', 'level 2: some problems' and 'level 3: extreme problems') for each dimension (mobility, self-care, usual activities, pain/discomfort, anxiety/ depression) as well as the distribution of patients in the dichotomized EQ-5D levels ['no problems' (level 1) and 'problems' (levels 2 and 3)] will be presented in frequency tables (N, %) for all patients with available data. Descriptive statistical measures will be calculated for the EQ-VAS score at each predefined study time-point.

The McNemar's test will be used in order to evaluate the change in the levels ('with problems'/ 'no problems') of each dimension between enrolment and the post-baseline visits.

Descriptive statistics of the EQ-VAS will be presented for each study visit as well as for the observed changes in the EQ-VAS from the enrolment visit to each post-baseline study time-point; while the paired t-test or the Wilcoxon signed rank test will be used to assess the statistical significance of the change.

The distribution of patients in the different ECOG performance status levels at every study time-point will be presented in frequency tables (N, %). Additionally, changes in the status of patients from baseline to post-baseline evaluations will be depicted in shift tables.

Adherence to treatment with afatinib as well as the proportions of patients who discontinued or interrupted treatment, and those who underwent any dose modifications along with the type of dosage modifications and reasons for these, will be analysed in a descriptive manner.

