## **11.6 STUDY SIZE**

Sample size calculation has been based on study's primary endpoint, which involves the determination of the proportion of study population with clinically meaningful improvement in the LCSS ASBI score over a 6-month treatment period.

Due to the lack of published data on the effect of afatinib on symptom burden using the LCSS, the worst case scenario has been taken into account, i.e., that the proportion of patients experiencing symptom improvement (*as defined in Section 11.1.3.1*) after 6 months of therapy will be approximately 0.50. Consequently, the assessment of 96 patients is required to estimate the aforementioned proportion with a margin of error not exceeding 0.10 which represents a scientifically acceptable level of precision of the estimate [95% CI: 0.40-0.60;  $\alpha$ : 0.05; Relative Standard Error (RSE): 10.21%]. This means that for any proportion between 0.05 and 0.95, the precision will range from 0.04 to 0.10 at a 95% confidence limit. The sample size determination has been performed using the statistical software package SAS v9.4 (SAS Institute, Cary, NC).

In order to control for an estimated 25% drop out/non-evaluable rate, 128 patients are finally required in order to ensure the aforementioned sample size for the final statistical analysis.

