## **11.8 DATA ANALYSIS**

The study is not aimed to confirm or reject any pre-defined hypotheses; therefore statistical analyses will be of explorative and descriptive nature.

Continuous variables will be summarized with the use of descriptive statistical measures (mean value, standard deviation, median and extreme values) and categorical/distinct variables will be displayed as frequency tables (N, %). The normality of distribution of continuous variables will be examined using the Shapiro-Wilk test in order to determine whether or not to use parametric methods for the analysis of the sample data.

Differences between the mean values of continuous variables will be evaluated using the paired t-test or the non-parametric analogue (i.e., Wilcoxon signed rank test).

All statistical tests will be two-sided and will be performed at a 0.05 significance level. The exact p-values will be reported, even for non-significant results, rounded to three (3) decimals unless the p-value is less than 0.001 (in such case P<0.001 will be reported). No adjustment for multiplicity of testing will be performed.

A SAP comprising a comprehensive and detailed description of the statistical methodology applied for the purposes of the interim and final analysis along with imputation methods for missing data will be prepared prior to database lock.

Statistical analysis will be conducted using a validated statistical software package [e.g., Statistical Analysis System (SAS)].

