## 3 DATA ANALYSIS CONSIDERATIONS

### 3.1 General presentation of summaries and analyses

Statistical analysis and generation of tables and patient data listings will be performed using SAS® statistical analysis software (the most updated version at the time of analysis onset). Figures will be created by validated graph programs, such as SAS® and/or Microsoft Excel.

Summary statistics will consist of frequency tables ( $n_{pt}$ , %) for categorical variables. For continuous variables, descriptive statistics [number of patients with available observations ( $n_{pt}$ ), number of missing observations ( $n_{miss}$ ), mean, standard deviation (SD), median, 25th and 75th percentiles, minimum (min) and maximum (max)] will be tabulated.

The normality of distribution of continuous variables will be examined using the Shapiro-Wilk test. Concerning binomial proportions 95% CIs will be derived from Wald confidence limits for binomial proportions. In order to examine the differences in the values of continuous variables, the paired t-test or the Wilcoxon signed-rank test for two dependent samples will be used. The association between categorical variables will be assessed with the use of the McNemar's test for paired samples.

Potentially, linear mixed-effects models for repeated-measures will be fitted in order to describe the trend of continuous variables over time. The impact of patient characteristics on variables of interest will be evaluated with the use of logistic regression models for dichotomous outcome variables. Pertaining to data presentation, when reporting relative frequencies or other percent values the following rules will apply:

- ✓ For values where all patients fulfil a certain criterion, the percent value will be displayed as 100.0.

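### Visit-by-visit tests of LCSS, ASBI and EQ-VAS change in patients still observed may overstate later improvement, and the longitudinal model that could help is not firmly specified

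*Protocol*

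**What the plan says.** Under Protocol 11.8.3, mean change in total LCSS "will be calculated from enrolment to all available subsequent study visits and will be examined for statistical significance" with a paired t-test or its non-parametric analogue. ASBI and each LCSS domain are treated similarly, and EQ-VAS change gets a paired t-test or Wilcoxon test. Protocol 11.8.1 and SAP 3.5 base the secondary analyses on subsets with available data. Protocol 11.8 adds: "All statistical tests will be two-sided and will be performed at a 0.05 significance level" and "No adjustment for multiplicity of testing will be performed".

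The protocol abstract (study design) and SAP 2.3 end observation at 48 months or, if earlier, at progression, death, unacceptable toxicity, withdrawal of consent, study completion or the physician's decision. SAP 3.2 sets visits at months 2, 4, 6, 8, 10 and 12, then every 6 months to month 48, each with a window of ±3 weeks. SAP 3.3 counts assessments at premature withdrawal only if they were collected within the predefined time points.

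On longitudinal modelling the text is uneven. Protocol 11.8.3 plans linear mixed models where applicable, for LCSS and ASBI, "in order to estimate the monthly predicted change in the aforementioned scores". SAP 3.1 is equally tentative: "Potentially, linear mixed-effects models for repeated-measures will be fitted in order to describe the trend of continuous variables over time". The data-analysis part of the protocol abstract states the models without a condition. The endpoint lists (Protocol 11.1.3.2, SAP 2.1.2) promise a longitudinal analysis of the LCSS scores outright. No mixed model is named for EQ-VAS in Protocol 11.8.3.

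**The concern.** Each paired test compares the patients present at a visit with their own enrolment scores. Because progression ends observation, the group at month 12 or 24 is not the group that started treatment. If patients whose symptoms worsen leave sooner, mean improvement among those remaining grows even when no individual's expected course changes. A reader could take this as benefit building up over time.

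The protocol's background makes symptom-related exit plausible. Section 9.2.1 reports that longer PFS went together with better HRQoL and longer symptom control, and Section 9.1 reports that quality of life predicts survival.

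A mixed model using every patient's scores could reduce the problem. As worded, though, it may not be run, omits EQ-VAS, and aims at one monthly figure. Such a figure describes poorly a score that falls early and then levels off. The stake is the interpretation of secondary results that Section 9.3 intends to assist clinicians' decisions.

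**Working it through.** **1. The plan's own figure.** The only sample-size statement concerns the primary proportion, which "after 6 months of therapy will be approximately 0.50", estimated "with a margin of error not exceeding 0.10". n = 1.96² × 0.25 / 0.10² = 96.04, stated as 96. Half-width at 96 = 1.96 × √(0.25/96) = 0.100. RSE = √(0.25/96) / 0.50 = 10.21%. Enrolled = 96 / 0.75 = 128. All reproduce, and none is affected by this point. No precision is stated for the change scores.

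**2. Who is left at each visit.** Inputs are PFS on afatinib of 13.6 months (median) and 11.0 months (called a mean; treated here as a median), both from Protocol 9.2.1. The proportion who have left by month t is 1 − 0.5^(t/median).
- Month 12: 1 − 0.5^(12/11.0) = 53%; 1 − 0.5^(12/13.6) = 46%.
- Month 24: 1 − 0.5^(24/11.0) = 78%; 1 − 0.5^(24/13.6) = 71%.

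If 11.0 really is an exponential mean, losses are larger: 1 − e^(−12/11) = 66% at month 12 and 1 − e^(−24/11) = 89% at month 24.

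The expected number observed also reflects late enrolment (uniform accrual over 48 months, study end at 60), with factor min(1, (60 − t)/48):

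| Month | PFS 11.0 | PFS 13.6 |
|---|---|---|
| 6 | 88 | 94 |
| 12 | 60 | 69 |
| 24 | 21 | 28 |
| 36 | 7 | 10 |
| 48 | 2 | 3 |

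For example, month 24 with PFS 11.0: 128 × 0.220 × 0.75 = 21. The month-6 values are close to the 96 implied by the plan's 25% loss.

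**3. Effect on visit means.** This was a simulation with 200,000 patients per scenario and a true mean change of -10 at every post-baseline visit. Assumed inputs, not in the documents: between-patient SD of change 10, slope SD 0.5 per month, residual SD 8. The exit hazard is multiplied by exp(γ × deviation/10), with γ from 0 to 0.7. A patient 10 points worse than average therefore has a hazard 1.22 (γ = 0.2) to 2.01 (γ = 0.7) times as high. Exit was driven either by the last observed score or by the current unobserved one, and both PFS values were used.

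| Month | γ = 0 | γ = 0.2 to 0.7 |
|---|---|---|
| 6 | -10.0 | -10.4 to -12.8 |
| 12 | -9.9 to -10.0 | -11.2 to -15.5 |
| 24 | -10.0 to -10.1 | -13.6 to -22.2 |

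**4. What a mixed model would give.** Simulated studies of 128 patients (40 replicates), true change -10 from month 2, PFS 11.0, γ = 0.4, exit depending on observed scores:

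| Month | Visit mean | Model, visit as category |
|---|---|---|
| 2 | -10.0 | -10.0 |
| 6 | -11.3 | -10.1 |
| 12 | -13.6 | -9.7 |
| 24 | -19.8 | -7.7 |

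The month-24 model value rests on about 22 patients per study and is imprecise. A model with one straight line in time gave -0.42 per month, so a predicted change of about -0.8 at month 2 and -5 at month 12. With no symptom-related exit it gave -0.53 per month, or 2 × -0.53 = -1.1 at month 2 against a true -10.

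**5. Limit of the model.** In a separate run with a true constant change of -8 and exit driven by unobserved worsening, the month-12 paired mean was -11.8 and the categorical-visit model gave -11.2. It removed 0.6 of a 3.8-point bias.

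**6. Withdrawal assessments.** A ±3-week window is 42 days. That is 42/60.9 = 69% of each 2-month interval but 42/182.6 = 23% of each 6-month interval. After year 1, many scores taken at exit could fall outside a window.

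**The case against.** The strongest reply is that the study calls itself explorative and descriptive, and change among patients still on treatment is a legitimate descriptive quantity. That stands, provided it is labelled as such. SAP 3.1 and 5.1 already plan the numbers observed and missing, completion of each visit and reasons for withdrawal, and in-window withdrawal scores are kept. The mixed model has a debatable target of its own: change as if patients who progressed or died had continued to be measured.

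Four stronger readings are tempting but not supported.
- A reader might infer that an early drop would be hidden. It would not: the planned mean changes at months 2, 4 and 6 would show it. Only a single slope would miss it.
- A reader might infer that the longitudinal model is merely optional. The abstract and endpoint lists are unconditional, and SAP Section 8, to which SAP 4.2 and 7 refer for the primary-endpoint and adherence analyses, was not in the text available. The SAP also abbreviates the Akaike criterion without using it in the visible text, so modelling detail may sit there. Likewise, a straight line in time is an inference from the monthly target, since a linear mixed model is only a class of model.
- A reader might infer that later improvement is certainly overstated. With γ = 0 there is no bias.
- A reader might infer that the normality check, made "in order to determine whether or not to use parametric methods for the analysis of the sample data", is a comparable fault. It could let the test differ between visits, but no harm has been shown and it is secondary here.

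**Conclusion.** The point holds in conditional form. Visit-wise available-case tests combined with exit at progression may overstate later improvement in LCSS, ASBI and EQ-VAS. About half of patients are expected to have left by month 12 and 71–78% by month 24, taking the cited PFS values as exponential medians. Under the assumed variances and dropout strengths, the overstatement is about 1 to 5.5 points at month 12 and 4 to 12 points at month 24. The upper end exceeds the plan's own 10-point threshold for meaningful change. The direction depends on exit being related to symptoms, which the protocol's background suggests but does not establish.

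Separately, the documents disagree on whether the longitudinal model is firm, and the visible text gives EQ-VAS none. The primary 6-month endpoint and the sample size are outside this point.

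**What to change.** In Protocol 11.8.3 and the SAP, including Section 8 if it does not already do this:
- Make the mixed model firm for LCSS, ASBI and EQ-VAS, and align the abstract, endpoint lists, Protocol 11.8.3 and SAP 3.1.
- Enter visit as a categorical factor, include every patient with an enrolment score and at least one later score, and report change with a 95% CI per visit.
- Keep the paired changes as descriptive results, labelled as patients still on study, with the number observed beside each.
- Add one simple sensitivity analysis for dropout related to progression or worsening.

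The cost is SAP wording and a standard SAS model, with no new data. The limits should be stated in the plan: the model assumes missing at random, corrects only part of the bias if exit depends on unobserved worsening, and treats patients who progressed or died as if measurement had continued. With about 7 to 10 patients expected at month 36 and 2 to 3 at month 48, late visits may need pooling.

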#### **11.8.4 Analyses for the safety data**

All recorded AEs will be mapped by system organ class (SOC) and preferred term (PT) according to MedDRA (*most updated version at the point of coding*).

The number and proportion of patients experiencing any serious or non-serious adverse event will be calculated by SOC and PT.

Specifically, the following data will be tabulated:

- Number and proportion of patients experiencing a serious AE (SAE) by SOC and PT.
- Number and proportion of patients experiencing a non-serious AE (NSAE) by SOC and PT.
- Distribution of AEs by National Cancer Institute (NCI) Common Toxicity Criteria for Adverse Events (CTCAE) toxicity grade classification and causal relationship to study treatment.

Additionally, the exposure adjusted incidence rates (EAIRs) along with the respective 95% CIs will be calculated for the following patient subpopulations: those experiencing at least one SAE, at least one NSAE.

Available data from other safety-related evaluations (systolic and diastolic arterial blood pressure, respiratory rate and pulse rate) will be summarized descriptively per visit or when they occurred, along with the respective change from baseline to all post-baseline visits.

#### **11.8.5 Drug exposure**

The exposure ( $D_{Exp}$ ) to afatinib treatment will be calculated using the number of days on afatinib, i.e. duration since treatment onset ( $date_{First}$ ) until the date of last treatment administration or until the last date with available data ( $date_{Last}$ ) according to the following formula.

$$D_{Exp} = (date_{Last} - date_{First}) + 1$$

Descriptive statistics (n, mean, standard deviation, median, range) will be calculated for the duration of afatinib treatment for all patients of FAS.

#### **11.8.6 Additional analyses**

Descriptive statistics regarding sociodemographic data such as gender, race, smoking history and educational background will be displayed in frequency tables (N, %).

Continuous variables concerning demographics and anthropometric characteristics such as age, body weight, and height as recorded at the enrolment visit will be presented with

mean, SD, median, minimum and maximum values. Quantitative variables will be presented with absolute and relative frequencies.

The number and percentage of patients with at least one medical condition as recorded at the enrollment visit will be calculated. Additionally, the depicting reported terms will be coded by MedDRA (*the most updated version available at the point of coding*) while SOC and PT will be tabulated in a frequency table (N,%).

The number and percentages of patients receiving at least one concomitant medication will be calculated. Concomitant medications coded with the use of ATC Drug Classification dictionary by WHOCC in terms of therapeutic subgroup and chemical substance will be presented in frequency tables (N,%). Similar analyses methods will be performed for all therapies related to NSCLC prior to afatinib onset.

#### **11.8.7      Interim analysis**

Taking into consideration the long-term study duration as well as the current limited evidence on the real-world clinical outcomes of treatment with afatinib in patients with NSCLC, an interim analysis is planned to be performed after the first enrolled 40 patients (i.e., around one-third of the overall sample size) have completed the 6-month study observation period (i.e., have attended the 6-month study visit [V4] or have discontinued study participation, whichever occurs first).

The main purpose of the interim analysis is to gain preliminary information on the impact of afatinib in the study key outcome measures. No resultant decisions and actions will be taken in terms of the study progress as a consequence of the interim analysis. The interim analysis does not involve any stopping boundary for early stop due to efficacy or for sample size adjustment, thus no multiplicity adjustment will be performed.

The confidentiality of the interim analysis data will be controlled by assignment of the analysis to a statistical group that is independent of the Sponsor and investigators, i.e. is not otherwise involved in the study design or conduct. After completion of the analysis the results will be summarized in a synoptic interim CSR and distributed to the study Sponsor. The detailed interim analysis results will not be disclosed to the participating investigators until the overall study completion in order to account for the avoidance of any bias that may result from the premature disclosure and subjective interpretation of the preliminary findings. However, the preliminary results may be announced in the form of an abstract or poster/presentation in a descriptive manner, as per the Sponsor's decision; in such case, the minimum required information will be disclosed aiming at safeguarding the scientific integrity of the final study results.

#### **11.9      QUALITY CONTROL**

Proper quality control mechanisms and processes will be implemented in order to ensure data quality and integrity through the conduct of the study. All these procedures will be detailed in the study specific DMP and SAP.

The query management process for the eCRF-collected data will be handled on a real-time-basis through built-in edit and logic checks (validation rules) in the eCRF application. If any discrepancies (other than those predicted by the built-in validation

rules) arise before eCRF lock during source data verification (SDV) process (performed by the project monitor) or data review by the Data Manager, queries will be handled electronically through specific application's query functionality, whereas for discrepancies that may emerge after eCRF application lock, paper Data Clarification Forms (pDCF) will be issued manually, using Microsoft Word. For PRO-collected data no queries will be issued. After all data have been properly validated, the quality control procedure has been completed and database lock has been declared, the extracted file will be transferred to sponsor. Statistical analysis performance & CSR development will be performed by a designated CRO.

Statistical programming performed to generate the results as well as all-related documents and forms will be archived electronically.

e-CRF archivals for each participating site will be prepared in CD-ROMs by the designated CRO, upon study completion and will be distributed to the participating sites.

The study authorized representative will provide the investigators with a folder/file in which the study-related documents should be archived and maintained. All study documents should be stored in this file by the Investigator. The monitor of the study will regularly check the file to ensure that all relevant documents are maintained. The contents of the folder/file may be subjected to audit/inspection by a designated auditor, regulatory authorities or Hospital Institutional Review Boards (IRBs).

The designated CRO will assure database quality by reviewing the data entered into the CRFs by investigational staff for completeness and accuracy, and in accordance with the data validation plan. The [REDACTED] may perform quality control visits at study sites to ensure implementation of the study protocol and all relevant regulatory and BI procedures.

